Steroids often have adjusted dose regimens such that drug may be slowly increased or decreased over time and short acute treatment episodes are also possible. Such changes in dose over time will not be examined, however total cumulative dose will be examined in relation to outcomes of interest (see below).

Cumulative dose

For glucocorticoids used in COVID-19 indication, orally administered, if quantity is available, the formula to calculate the cumulative exposure in mg is described below:

$$Cumulative\ dose_{solid}[mg] = \sum_{all\ exposures} quantity \times amount_value [mg]$$

If the **quantity is missing**, the number of units per day for solid formulations are extracted. The cumulative exposure in mg can then be calculated using the following formula:

$$Cumulative\ dose_{solid}[mg] = \sum_{exposures} units\ per\ day \times amount_value [mg] \times duration$$

For intravenous administration (bolus administration), the dose administered each time will be counted.

$$Cumulative\ dose\ intravenous [mg] = \sum_{all\ exposures} amount_value [mg]$$

Exposure groups for incidence calculation (secondary objective 2 and 3)

For the incidence rates calculation, an on-treatment exposure will be considered with mutually exclusive groups to allow calculation of incidence rates.

Each person will be classified as belonging to one of the following mutually exclusive exposure groups at treatment index date following COVID-19 diagnosis:

- Use of systemic glucocorticoids without other treatments for COVID-19 (drug and respiratory support)
- Use of systemic glucocorticoids plus other treatments for COVID-19 (drug and respiratory support)
- Only other treatments and respiratory support with no systemic glucocorticoids

- No specific treatments for COVID-19 infection (other concomitant treatments for indications other than for COVID-19 are allowed)

A single prescription would be enough to consider the patient as exposed. See section 7.3.2.1 for description of 'other treatment for COVID-19' that are included.

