Only the first episode of exposure will be considered, patients being censored when they switch to another treatment (including switch to another glucocorticoid) or when follow up ends. Duration of follow-up for each treatment cohort will be summarized and will constitute the denominator for calculation of effect estimates. A persistence window of 7 days between drug utilization records for each study drug will be allowed considered as continuous exposure for the outcome's assessment.

In case that more than 70% of the patients are censored, a sensitivity approach will be applied for objectives 2 and 3 (see Section 7.7.8).

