7.7.3 Patient characteristics (secondary objective 1)

Summary descriptive statistics will be presented by the four cohorts (section 7.2.2) and *described both at diagnosis and treatment index dates in each cohort*. The following will be described at diagnosis date and also treatment index date: patient demographics and clinical characteristics. Where available, a description of COVID-19 illness onset (time to diagnosis), associated symptoms and time to hospitalization for COVID-19 infection will be presented.

Data will be further stratified by subgroups of special interest (see section 7.2.4).

7.7.4 Estimation of incidence of study adverse events of interest and disease outcomes (secondary objectives 2 and 3)

The crude incidence rate of the individual outcome relevant to each sub-cohort reported during person-time treated for each exposure group will be calculated. The crude person-time from relevant index date will be calculated for the following groups:

- Use of systemic glucocorticoids without other treatments for COVID-19 (drug and respiratory support)
- Use of systemic glucocorticoids plus other treatments for COVID-19 (drug and respiratory support)
- Only other treatments and respiratory support with no steroids
- No specific treatments for COVID-19 infection (other concomitant treatments are allowed are allowed)

Only the earliest eligible treatment is considered, and for patients who switch to another treatment (including switch to another glucocorticoid), their follow-up is censored at date of switching. The number and reasons for patients censoring will be reported.

We will calculate both, the incidence proportion and the incidence rate. The numerator for both (risk and rate) will be comprised of counts of incident events of interest during the person-time as defined above recorded during each cumulative interval and summed to reflect the cumulative count for the interval.

The crude cumulative incidence rate will be calculated according to the formula:

$$\frac{\text{Total number of patients on Rx with first event during cumulative interval of interest}}{\text{Total person-time at risk (days)}} \times 100$$

The crude incidence proportion will be calculated according to the formula:

$$\frac{\text{Total number of patients on Rx with first event during cumulative interval of interest}}{\text{Total population at risk at start of study period}} \times 100$$

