7.7.8 Sensitivity analysis

For objective 2 and 3, with regards to the reference group for incidence rates

As a sensitivity analysis, the reference group for incidence rates will be replaced with ‘other immunotherapies’ (see Appendix 3 for details).

For prevalent users’ cohorts, the definition of remote users:

A sensitivity analysis to exclude those patients for whom short term duration of corticosteroid use (14 days) is identified prior to COVID-19 diagnosis.

For objectives 2 and 3, if the number of patients censored due to switching is higher than 70%, a sensitivity analysis will be performed, namely an intention to treat approach (ITT), such that after initial exposure is defined to allocate patients to one of the four treatment groups, the denominator is then person-time observed (irrespective of treatment status), rather than person-time treated.

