7.9 Limitations of the Research Methods

7.9.1 Study design limitation

COVID-19 diagnosis misclassification – the diagnosis of COVID-19 in absence of confirmatory test has a high likelihood to be misclassified as the disease symptoms are unspecific. This misclassification is more likely for patients treated in primary care, e.g., those with milder symptoms. In addition, with regards to the availability of results of PCR test for SARS-CoV-2, this is currently available in only one database (SIDIAP).

- **Mitigation:** Different definitions will be explored and compared as part of objective 4. We will base the main definition on definite diagnosis not on symptoms only and supplement with confirmatory tests when available

Confounding by indication and severity may occur when the different treatments are prescribed depending upon the physician's assessment of the patient's health status in relation to the outcome of interest. The risk of this confounding is high due to glucocorticoids being indicated in severe COVID-19 cases only and therefore correlated with the increase in severity.

- **Mitigation:** No comparative analysis will be performed. This confounding needs to be considered when interpreting the incidence rates obtained.

Selection bias occurs when there is a selective recruitment into the study of subjects that are not representative of the population intended to be studied, so that the association between exposure and outcome of interest is different in the included and excluded population.

- **Mitigation:** Minimal exclusion criteria will be used. In addition, we have included data sources with large or whole national coverage and both ambulatory and hospital setting.

Exposure to glucocorticoids in hospital setting might be underrepresented as glucocorticoid might be captured only as ward stock and not as individual dispensation.

On-treatment exposure classification was considered suitable for this study in order to facilitate comparison with clinical trials results. However, this way of classifying exposure does not consider subsequent treatments and might miss a deterioration of disease.

The **short duration of follow-up** will allow only the capture of acute adverse events.

Prescribing patterns of corticosteroids over time

Due to the short study period (1 year) any time series analysis cannot be undertaken, and the observed trends cannot be confirmed.

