If exposure to glucocorticoids as second or third treatment occurs very often, a large proportion of patients will be censored, leading to limited data to assess the outcomes of interest.

Mitigation – an ITT sensitivity analysis is proposed in case censoring is very large (>70%)

7.9.2 **Databases related limitations**

Linkage between primary and secondary care

Seven out of eight databases will not have linkage between primary and secondary setting, and a consequence of this is that patient follow up time will be fragmented. Especially in the hospital setting, the access to medical history of the patient is limited and the patients who had prior exposure of glucocorticoids in primary care risk to be misclassified as naïve users.

Primary care databases

Severe outcomes that lead to hospitalization are less likely to be captured., although hospitalization is captured in some of the primary care databases.

If patients are free to change general practitioners and they are not tracked across different GPs or if they are treated. In private practice, their exposure will be underestimated and the follow up will be fragmented.

As the hospital and ambulatory settings are not linked, patients who had prior exposure of glucocorticoids in hospitals will be misclassified as naïve users.

Hospital setting databases

As the lookback period in the hospital setting is in general absent or reduced, there will be an under-ascertainment of baseline comorbidities.

Mortality data

The mortality information (vital status) is under-captured in some data sources. Three of them, DA Germany, LPD France and LPD Italy do not record vital status at all. For SIDIAP, the vital status comes from a regional mortality register while for HM Hospitales, the vital status comes directly from hospital records. For IMRD UK and IPCI, the vitals status information comes from GP recording.

Section 8.0 Protection of Human Subjects

For this study, participants from various EU member states will process personal data from individuals which is collected in national/regional electronic health record databases. Due to the sensitive nature of this personal medical data, it is important to be fully aware of ethical and regulatory aspects and to strive to take all reasonable measures to ensure compliance with ethical and regulatory issues on privacy.

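### Starting a listed treatment for an emerging outcome may censor the patient before the event is coded, and the ITT analysis that would show this waits for a 70% data-volume trigger

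*Protocol*

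**What the plan says.** **Censoring rule.** Objectives 2 and 3 use on-treatment person-time. Section 7.3.2.3 says "Only the first episode of exposure will be considered, patients being censored when they switch to another treatment (including switch to another glucocorticoid"), or when follow-up ends. Section 7.7.4 repeats it for switchers: "their follow-up is censored at date of switching".

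**What counts as another treatment.** Section 7.3.2.3 defines four mutually exclusive groups by steroids, other COVID-19 drugs and respiratory support, and one prescription is enough for exposure. Section 7.3.2.2 identifies the other drugs by list membership, with no time window or indication test. In the untreated group, "other concomitant treatments for indications other than for COVID-19 are allowed".

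**The ITT analysis.** Section 7.3.2.3: "In case that more than 70% of the patients are censored, a sensitivity approach will be applied for objectives 2 and 3". Section 7.7.8 words the condition differently: "if the number of patients censored due to switching is higher than 70" per cent. In that case "the denominator is then person-time observed (irrespective of treatment status), rather than person-time treated". Section 7.9.1 gives the reason for the threshold: "a large proportion of patients will be censored, leading to limited data to assess the outcomes of interest".

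**What is already conceded.** On the on-treatment approach, section 7.9.1 says that "this way of classifying exposure does not consider subsequent treatments and might miss a deterioration of disease". Section 7.7.4 will report the number of patients censored and the reasons.

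**The concern.** Several drugs in Appendix 3 are ordinary treatment for outcomes counted in sections 7.3.3 and 7.3.4: amoxicillin, fluoroquinolones and ceftriaxone for bacterial infection; metformin for hyperglycaemia; ACE inhibitors, angiotensin receptor blockers and thiazides for hypertension; antithrombotics for venous thromboembolism; H2-blockers for gastritis and ulcer. Respiratory support helps define the exposure groups, while mechanical ventilation is an outcome in the hospital cohorts. One clinical event can therefore supply both the censoring date and the outcome.

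If the prescription or procedure is recorded first, the patient leaves follow-up and the event is not counted. Such censoring is informative, and it lowers that group's own descriptive rate. Reporting reasons for censoring does not show how the rate would change. The ITT rates would, but their trigger measures how many patients are censored and does not ask whether the censoring is related to the outcome.

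**Working it through.** The protocol states no event rate, no q and no derivation of the 70%, so there is no figure to reproduce. The rates, q and lags below are assumptions; the follow-up times (30 and 90 days) and the threshold come from the protocol.

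**1. Size of the loss.** Take a constant true event rate λ, and let q be the share of events with a listed treatment recorded before the code. Those events become censorings and the rest are counted, so the observed rate is about (1 − q)λ. For λ = 1.0 per 1,000 patient-days:

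| q | observed rate per 1,000 patient-days |
|---|---|
| 0% | 1.00 |
| 10% | 0.90 |
| 30% | 0.70 |
| 50% | 0.50 |

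A daily simulation (2 million patients, drug 3 days before the code) gave 0.50 on treatment against 1.00 under ITT at q = 50%. Only 1.6% of patients were censored for this reason by 30 days and 4.4% by 90 days. In the steroid-only group, if add-ons censor and treatment lasts 17 days (the 10-day maximum plus the 7-day persistence window), q = 50% again gave 0.50, with 1.0% censored for this reason.

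**2. Can outcome-driven censoring reach 70%?** For one outcome with no other switching, the share censored for this reason is about q × (1 − exp(−λT)), so it cannot much exceed the event risk:

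| λ per 1,000 patient-days | risk at 30 days | risk at 90 days |
|---|---|---|
| 1 | 1 − exp(−0.03) = 3.0% | 1 − exp(−0.09) = 8.6% |
| 5 | 1 − exp(−0.15) = 13.9% | 1 − exp(−0.45) = 36.2% |

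A 70% event risk needs λ = −ln(0.3)/T: 13.4 per 1,000 patient-days over 90 days, or 40.1 over 30 days, with q = 100%.

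**3. With unrelated switching added.** At λ = 1 and q = 30%, with about 30% unrelated switching over 90 days, the observed rate was 0.70 against 1.00 under ITT. Total switching was 31%, so the section 7.7.8 trigger stays silent. Conversely, with unrelated switching of 71–73% and q = 0, the trigger fires although the observed rate is 0.95–1.00 against 1.00.

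A second simulation used 400,000 untreated patients per scenario, 90-day risk 2–20%, q 0–100%, a 5-day lag and background switching 0–60%. The ratio to ITT was about 0.75, 0.50 and 0.20 at q = 25%, 50% and 80%. Switching reached at most 68.5% in the 60 scenarios; that ceiling partly reflects the cap on assumed background switching.

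**4. Same-day records.** With drug and code on one date and q = 50%, the rate is 0.50 if censoring is applied first and 1.00 if the event is counted first. Sections 7.3.2.3 and 7.7.4 do not say which.

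**5. The two trigger wordings.** Suppose nobody switches and reaching the end of follow-up counts as censoring. More than 70% are then censored whenever λ is below −ln(0.7)/T, which is 4.0 per 1,000 patient-days over 90 days or 11.9 over 30 days. The section 7.3.2.3 wording would then fire; the section 7.7.8 wording would not.

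**The case against.** **Switching is undefined.** A patient on nothing has no treatment to switch from, and an add-on to a continuing steroid need not be a switch. This stands as a limit: the mechanism is conditional. For the untreated group, though, the groups are mutually exclusive and on-treatment, and starting a listed treatment is the only switch available.

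**Drugs for other indications are allowed in the untreated group.** On its face this protects a patient given metformin for hyperglycaemia. But section 7.3.2.1 says indication is not captured in the available databases. Section 7.4 lists it only for LPD Italy and IPCI, so the exception might work there; elsewhere the protocol gives no rule for applying it.

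**Scope.** The opening of section 7.3.3 speaks of patients given glucocorticoids or alternative therapies, which omits the untreated. Section 7.7.4 computes the rates for all four groups, so this does not settle the matter.

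**No document shows that the drug precedes the code.** This is correct. In consultation records the two may share a date, and then the tie rule decides.

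**The choice is disclosed and the study is non-comparative.** Also correct, but the loss is to each group's own rate, and the disclosure does not quantify it.

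**Stronger readings a reader might infer.** One is that the trigger can never be reached when q is below 70%. That holds only for one outcome with no other switching: four independent outcomes of 60% risk each, at q = 50%, give 1 − 0.7⁴ = 76% censored. Unrelated switching or empirical prescribing can also push the total past 70%. Another is that the two trigger wordings are a serious contradiction. Section 7.3.2.3 points to section 7.7.8, section 7.9.1 is about later treatments, and section 7.2.3 does not list reaching 90 days among its censoring criteria. Censoring due to switching is therefore probably what is meant.

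**Conclusion.** The concern holds in conditional form. If starting a listed treatment counts as a switch, on-treatment rates of outcomes treated from the list may be understated by a factor of about (1 − q). This is clearest in the untreated group; the steroid-only group is affected only if add-ons censor. The table in the working illustrates the range and is not an estimate: q is not documented, and q = 0 means no bias, so a reader should not infer that the rates will in fact be understated.

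Outcomes without a listed treatment, such as psychosis and myopathy, are unaffected, and unlisted drugs such as insulin, proton-pump inhibitors or beta-blockers do not censor.

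The firmer part is the safeguard. The protocol ties the ITT analysis to the volume of censoring, so it can stay unrun when censoring is outcome-driven and run when it is not. The differing trigger wording is secondary. This should be changed, with medium confidence in its practical size.

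**What to change.** 1. In sections 7.3.2.3 and 7.7.8, drop the 70% condition and always report ITT person-time rates, labelled as such, beside the on-treatment rates. State that events and person-time are counted over the same observed period: section 7.7.8 redefines only the denominator, while the section 7.7.4 numerators are restricted to patients on treatment. This also disposes of the two trigger wordings.
2. In section 7.7.4, count an event coded on the switch date as occurring before censoring.
3. Optionally, state whether starting a first listed treatment, or adding one while the index treatment continues, is a switch.

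The cost is two or three sentences and one further set of rates from data already held; no outcome-specific drug list is needed. The drawback is that ITT rates keep person-time after a later treatment in the original group, which is why the label matters.

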7.2.3 Follow-up

Two index date definitions will be applied as appropriate for each objective.

- Diagnosis index date is defined as a positive PCR test for SARS-CoV-2 (labCOVID-19) or a confirmed COVID-19 diagnosis(diagCOVID-19) whichever is the earliest.
- Treatment index date is defined as start of first systemic glucocorticoid treatment episode specifically for the treatment of COVID-19, irrespective of whether the patient is a prevalent or naïve user.

Follow up for all patients will begin from the index date until they experience the outcome of interest (endpoint, depending on the objective) or until cohort exit (date of censoring). The patients will be followed up for maximum 90 days or until censoring occurs, censoring criteria are:

- death
- patient exit (deregister) from a contributing data provider (GP practice)
- end of the database's data collection
- end of study period (latest data cut-off)

The lookback window for evaluating risk factors, medical history is 365 days and will be applied only to outpatient cohorts.

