7.3.2.1 Glucocorticoids

Glucocorticoids used in COVID-19 indication

The primary treatment group of interest is based on exposure to systemic glucocorticoids. The following drugs will be considered as being used for COVID-19 diagnosis:

- Dexamethasone (H02AB02)
- Prednisone (H02AB07)
- Prednisolone (H02AB06)
- Methylprednisolone (H02AB04)
- Hydrocortisone (H02AB09)

Only glucocorticoids which were investigated in clinical trials (13,21) or are recommended by clinical guidelines are included (22–24) to avoid misclassification of steroids used for other conditions. As indication is not captured in the available databases, a glucocorticoid treatment will be considered to have been initiated for COVID-19 treatment if:

For incident users

- The glucocorticoid treatment was initiated between 2 before and 30 days after COVID-19 diagnosis date (21)
- It is one of the five glucocorticoids recommended for COVID-19 as above

For prevalent users

- The glucocorticoid treatment was initiated between 2 before and 30 days after COVID-19 diagnosis date
- It is one of the five glucocorticoids recommended for COVID-19 as above
- The glucocorticoid started after COVID-19 diagnosis differs from the chronically used glucocorticoids OR there is a change in dose or schedule of administration compared to the prevalent use, occurred after COVID-19 diagnosis.

Glucocorticoids for pre-existing conditions

For the prevalent users, any steroid in the ATC class H02 glucocorticoids for systemic use will be considered. A patient is defined as a systemic glucocorticoids prevalent user if it has at least one prior exposure to systemic² glucocorticoids in the 120 days prior to diagnosis index date.

For the description of prevalent users of glucocorticoids, categories of use will be created based on proportion of days covered (PDC) during the lookback period. PDC is calculated as the number of days in period covered by prescriptions divided by number of days in the period.

- PDC > 85% as heavy user
- PDC 50-85% as moderate user
- less than 50% PDC as light user

Another categorization of prevalent glucocorticoids user will be based on how recently in the past the last prescription was observed:

- current use (concomitant on date of COVID-19 diagnosis)
- recent use (between 15-30 days before date of COVID-19 diagnosis)
- remote use (use ended more than 30 days before date of COVID-19 diagnosis)

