For each sub-cohort and type of person-time the numerator for each time frame will contain the number of patients for whom an outcome has been recorded in that time frame since the onset of that type of person-time. The crude incidence rate of each outcome within the relevant sub-cohort will be expressed as number of cases per 1,000 patient-days at risk.

The cumulative incidence rate will be reported at the end of follow-up (30 and 90 days).

The person-time estimation and the calculation of the crude incidence rate for secondary objectives 2 and 3 will be similar except for the outcomes being considered in each case. For secondary objective 2, adverse events of interest for glucocorticoids (listed in Section 7.3.3) will be the outcome, and for secondary objective 3 mortality and other disease outcomes (Section 7.3.4) will be the outcome.

Both stratification and adjustment will be used as a method to deal with confounders.

In order to examine risk factors of the outcomes of interest, data will also be stratified by subgroups of interest (7.2.4) and stratum-specific crude incidence rates will be calculated. The stratification variables include the healthcare setting, glucocorticoid user type (naive, prevalent) treatment groups and subgroups of special interest.

Separate Cox regression models will be used to estimate adjusted cause-specific HR³ (in order to account for competing events) for each outcome **within** the following four treatment groups:

- Use of systemic glucocorticoids without other treatments for COVID-19 (drug and respiratory support)
- Use of systemic glucocorticoids plus other treatments for COVID-19 (drug and respiratory support)
- Only other treatments and respiratory support with no systemic glucocorticoids

³ Cause-specific HR are to be interpreted as instantaneous risk estimates and not as cumulative risk estimates; cumulative risks estimates are subject to competing events <https://pubmed.ncbi.nlm.nih.gov/30012114/>

- No specific treatments for COVID-19 infection (other concomitant treatments for indications other than for COVID-19 are allowed)

In addition to stratified analysis, for each of the above four treatment groups, two sets of Cox regression models will be run:

- 1) A model that is adjusted for a list of predefined confounders
- 2) A model that is adjusted for a high dimension propensity score that is derived through large-scale modelling, using all available covariates in each dataset (Section 7.7.5)

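### Follow-up is censored at a change of glucocorticoid molecule although the exposure groups are defined for the class, so class-exposed time and events are discarded

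*Protocol*

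**What the plan says.** Protocol Section 7.3.2.3 sets up four mutually exclusive exposure groups for objectives 2 and 3. The two that contain glucocorticoids are "Use of systemic glucocorticoids without other treatments for COVID-19 (drug and respiratory support") and "Use of systemic glucocorticoids plus other treatments for COVID-19 (drug and respiratory support"). Section 7.7.4 repeats them for the crude rates and for the Cox models. None of the four is defined by substance. Section 7.3.2.1 lists five molecules, and a qualifying drug need only meet the condition "It is one of the five glucocorticoids recommended for COVID-19 as above".

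The censoring rule in Section 7.3.2.3 has "patients being censored when they switch to another treatment (including switch to another glucocorticoid) or when follow up ends". Section 7.7.4 says the same: "for patients who switch to another treatment (including switch to another glucocorticoid), their follow-up is censored at date of switching". Only the first exposure episode counts, so a switcher does not re-enter. The 7-day persistence window is set separately for each study drug.

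The general rule in Section 7.2.3 reads "The patients will be followed up for maximum 90 days or until censoring occurs, censoring criteria are", followed by death, deregistration, end of data collection and end of study period. Switching is not on that list.

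On reporting, Section 7.7.4 states "The cumulative incidence rate will be reported at the end of follow-up (30 and 90 days"). The denominator of the incidence proportion is "Total population at risk at start of study period".

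**The concern.** The group label and the censoring rule work at different levels. The label asks what happens while a patient is on any systemic glucocorticoid. The rule answers for the time up to the first change of molecule. A patient who changes molecule has not left the group, but everything observed afterwards is dropped from it.

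Two results are at stake. The incidence proportion keeps the switcher in its denominator and loses the switcher's later events. The incidence rate and the cause-specific hazard need censoring that is unrelated to prognosis, and a change of molecule may well follow the clinical course. Section 7.9.1 itself links glucocorticoid use to severity and concedes that the on-treatment approach can miss deterioration. No correction for dependent censoring is described.

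**Working it through.** The protocol states no figure for this point, so there is none to reproduce. The check sets the text side by side and then scales the loss under stated assumptions.

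**1. Text.** Group membership depends on any systemic glucocorticoid, with or without other treatment (7.3.2.3, 7.7.4). A move between two of the five listed molecules changes neither condition. Follow-up nevertheless ends on that day, and a window set per drug cannot bridge two molecules. The cumulative-dose formula in 7.3.2.3 sums over all exposures, and that dose is to be examined against outcomes. Dose after a change of molecule would therefore count while outcomes after it would not.

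**2. Person-time lost.** Inputs: a 10-day course and a 7-day window, both figures appearing in 7.3.2.3. The 10 days is given there as a maximum for dexamethasone and is used here only for scale. Assumed: a share s changes molecule on day 5. Ignoring the few events before day 5, lost share = s × (L − 5)/L.

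| s | L = 10 | L = 10 + 7 = 17 |
|---|---|---|
| 10% | 0.10 × 5/10 = 5% | 0.10 × 12/17 = 7% |
| 30% | 15% | 21% |
| 50% | 25% | 35% |

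The protocol allows the 7 days between records and does not say that they extend risk time after the last one. L = 10 is therefore the safer column.

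**3. Incidence proportion, switching unrelated to prognosis.** With the same constant hazard before and after the change, events are lost in the same share as person-time, and the denominator does not shrink. The proportion is therefore understated by roughly the shares in step 2.

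A second illustration lets switching occur throughout 30 days. It borrows the 26% UK inpatient case fatality from Section 5.0 as the event risk. That figure has no stated time horizon, so 30 days is assumed, and patients are taken as class-exposed throughout. Daily hazard h = −ln(1 − 0.26)/30 = 0.01004. If 20% switch before an event, the events counted come to h/(h + σ) × [1 − exp(−30(h + σ))], where σ is the switch hazard that yields 20%. Here h + σ = 0.01874, giving 0.536 × 0.43 = 23.0% against a true 26.0%. At 40% switching the result is 19.8%, and at 69% it is 14.1%.

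**4. Rate, switching related to prognosis.** Same model, with hazard k × h after the change. The censored rate is always 10.04 per 1,000 patient-days. The class rate, with the ratio of censored to class rate in brackets, is:

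| Switching | k = 0.5 | k = 1 | k = 2 | k = 3 |
|---|---|---|---|---|
| 20% | 9.44 (1.06) | 10.04 (1.00) | 11.09 (0.91) | 11.97 (0.84) |
| 40% | 8.79 (1.14) | 10.04 (1.00) | 12.27 (0.82) | 14.17 (0.71) |
| 69% | 7.67 (1.31) | 10.04 (1.00) | 14.38 (0.70) | 18.23 (0.55) |

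The switch shares and k are assumptions; nothing in the protocol fixes them. The 69% row lies just under the 70% trigger for the intention-to-treat sensitivity analysis in 7.7.8, so switching at that level would not start it.

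**The case against.** The strongest defence is that the choice is deliberate and disclosed. Section 7.9.1 says the on-treatment classification was chosen to allow comparison with trial results and names its main weakness. Section 7.7.4 promises the numbers and reasons for censoring, and 7.7.8 offers an intention-to-treat analysis. Starting-dose cut-offs are substance-specific, and 7.7.7 speaks of drug-outcome pairs. This would support substance-specific groups. It does not support pooling five molecules under one label and then censoring movement within it, which the limitations section never mentions. The intention-to-treat analysis is conditional, and because it ignores treatment status altogether it is not the missing class-level on-treatment analysis.

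Several counter-arguments stand and limit the point:

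- The switching rule is general. The glucocorticoid clause is one instance, and a change of drug within the group on other treatments only is naturally read as a switch too. A fix confined to glucocorticoids could make censoring unequal across groups.
- Changes of molecule are likely to be seen mostly in hospital. Section 7.5 gives one hospital database with around 2,000 of 153,759 patients (2,000/153,759 = 1.3%). Apart from SIDIAP, the databases lack linkage between primary and secondary care.
- The study is descriptive, and treatment comparisons are out of scope, so no planned contrast is distorted.

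A reader might also infer more than the documents support:

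- **That class rates are systematically too low.** Step 4 shows that the direction reverses if switchers are recovering and that the rate is unbiased at k = 1.
- **That only patients who stayed on their first product are analysed.** Switchers contribute all time and events up to the change.
- **That any step-up or step-down is censored.** Nothing makes a dose change within one molecule a censoring event.
- **That extra censoring weakens the 70% safeguard.** It makes that analysis more likely to run.

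**Conclusion.** The mismatch is real and is fixed in the text of two sections. It touches the glucocorticoid-group rates, proportions and Cox models of objectives 2 and 3, but not the primary objective. That the incidence proportion is understated whenever some patients change molecule and later have an event on the class follows from the stated denominator alone. Bias in the rate and the hazard depends on whether switching tracks prognosis, which is plausible but not shown in the protocol.

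The size is unknown. With 10 to 50% changing molecule on day 5 of a 10-day course, 5 to 25% of class-exposed person-time is lost; the 30-day figures in steps 3 and 4 assume class exposure throughout and show direction more than expected size. The effect is probably concentrated in the hospital database. It should be corrected, chiefly because the correction is simple and the present rule does not estimate what the group label says.

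**What to change.** In Sections 7.3.2.3 and 7.7.4, delete the parenthesis that counts a move to another glucocorticoid as a switch. Add wording such as: *A change between systemic glucocorticoids is continued exposure in the same group, and the 7-day persistence window is applied at class level. A change of drug within the group on other treatments only is handled in the same way. Follow-up is censored at a switch that changes the exposure group.* Keep molecule-level censoring as a sensitivity analysis, or for a substance-specific table if one is produced.

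Two related passages should be aligned at the same time. The censoring list in 7.2.3 should refer to the switching rule. The 70% trigger should be worded alike in 7.3.2.3 (any censoring) and 7.7.8 (censoring due to switching).

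The cost is protocol wording, one change to how exposure eras are built, and one extra sensitivity run. The downside is that the class rate mixes substances, which the group label already says.
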